15.1 MTD (Primary Endpoint)

Analysis Set: DLT

The maximum tolerated dose (MTD) is defined as the highest dose combination for a given schedule that causes DLTs in no more than 33.3% of subjects by the end of Cycle 1. The DLT information will be based on "Adverse Events" CRF page with "Dose limiting toxicity?" = Yes.

The end of Cycle 1 is defined as 28 days after the start of study treatment from Cycle 1 Treatment Day 1.

A summary table of DLTs during the first cycle of study treatment, including the Lead-in Period, will be provided by dose group and overall with:

- Number of subjects with no DLT
- Number of subjects with one or more DLTs

The listing of DLTs will also be provided.

15.2 Adverse Events

Analysis Set: FAS/SAF

AEs will be summarized based on the information collected from the "Adverse Events" CRF page.

- Pretreatment AEs are defined as AEs that were reported or worsened after signing the informed consent form up to the start of study treatment (either VX-984 or PLD), including the Lead-in Period if available.
- Treatment-emergent adverse events (TEAEs) are defined as those events with onset dates occurring within the on-treatment period as defined in Section 15.
- Serious Adverse Events (SAEs): serious adverse events (serious adverse event = yes).
- Adverse Events Leading to permanent treatment discontinuation: (action taken = drug withdrawn).
- Adverse Events Leading to temporary treatment discontinuation: (action taken = drug interrupted).
- Adverse Events Leading to dose reduction: (action taken with study drug = dose reduced).
- Adverse Events Leading to Death: adverse event leading to death (AEs with Grade 5 or outcome "fatal" if Grade 5 not applicable).

All analyses described in Section 15.2 will be based on TEAEs if not otherwise specified.

Incomplete AE-related dates will be handled as follows:

- In case the onset date is missing completely or missing partially but the onset month and year, or the onset year are equal to the start of study drug then the onset date will be replaced by the minimum of start of study drug and AE resolution date.
- In all other cases the missing onset day or missing onset month will be replaced by 1.
- Incomplete stop dates will be replaced by the last day of the month (if day is missing only), if not resulting in a date later than the date of subject's death. In the latter case the date of death will be used to impute the incomplete stop date.
- In all other cases the incomplete stop date will not be imputed. If stop date of AE is after date of cut-off outcome of AE is ongoing at cut-off.
- Further information after cut-off (e.g. fatal outcome) might be taken from Safety database and included separately into the CSR.

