#### 12.3.5.1 Adverse Events

AEs will be coded according to MedDRA. The number and percentage of subjects experiencing an AE will be summarized by the MedDRA system organ class and preferred term, as well as by dose group, concurrent regimen and study part, and overall. AEs will be classified as pre-treatment or treatment-emergent.

**Pre-treatment AEs** are defined as AEs that were reported or worsened after signing the ICF up to the start of study drug dosing.

**Treatment-emergent AEs** are defined as AEs that were reported or worsened on or after the start of study drug dosing through the 28-day Safety Follow-up Visit.

Only TEAEs will be summarized in tables. All summaries of TEAEs will be presented by the severity of the AE and relationship to the study drug. Some rules that will apply to the summarization of AEs are (1) a subject with multiple occurrences of the same AE or a continuing AE will only be counted once; (2) only the maximum severity level will be presented in the severity summary; and (3) only the worst relationship level will be presented in the relationship summary.

AEs leading to death, serious adverse events (SAEs), dose interruption, and permanent discontinuation will be listed separately. All AEs through the Safety Follow-up Visit will be listed in an individual subject data listing, including pre-treatment AEs.

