#### 13.1.1.3 Documentation of Adverse Events

All AEs will be collected from the time ICF is signed until the following time points:

- For subjects who do not enroll: until time of screen failure (e.g., screen failure, withdrawal of consent)
- For enrolled subjects who have a Safety Follow-up Visit: through the Safety Follow-up Visit
- For enrolled subjects who do not have a Safety Follow-up Visit, the **earliest** of 28 days after the last dose of study drug.

All subjects will be queried, using non-leading questions, about the occurrence of AEs at each study visit. When possible, a constellation of signs and/or symptoms will be identified as 1 overall event or diagnosis. All AEs for enrolled subjects will be recorded in the CRF and source document. AEs for subjects who are screened but not subsequently enrolled in the study will be recorded only in the subject's source documents. The following data will be documented for each AE:

- Description of the event
- Classification of "serious" or "nonserious"
- Date of first occurrence and date of resolution (if applicable)
- Toxicity grade
- Causal relationship to study drug(s)
- Action taken
- Outcome
- Concomitant medication or other treatment given
- Indication of DLT (Part A).

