6.1 Final Analysis

All final, planned analyses identified in the Clinical Trial Protocol and in this IAP will be performed only after the last subject has completed the treatment phase of the trial with all trial data in-house, all data queries resolved, and the database locked.

A data review meeting will be held prior to database lock. In addition, no database can be locked until this IAP has been approved.

7 Changes to the Planned Analyses in the Clinical Trial Protocol

The following changes were made in this IAP.

- Due to management decision, Part B from the protocol will not be further pursued. Therefore only Part A from the protocol is covered in this IAP.
- Analysis of exploratory endpoints from the protocol will not be performed.
- Listings will be presented based on the same analysis population as used in corresponding tables, which deviates from the requirement from the protocol: "listings will include all subjects who were enrolled, regardless of whether or not they received study treatment."
- Analysis of PK will not be performed, concentrations of VX-984 and PLD will only be listed by subject and nominal time.
- The definition of Full Analysis Set (FAS) from the protocol, to be used for efficacy analyses, is not used in this IAP. The updated version of FAS is defined in Section 8.2.

Definition of FAS per protocol: The FAS is defined as all subjects who received at least 1 cycle of study drug and have a baseline scan.

8 Protocol Deviations and Analysis Sets

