On-treatment period is defined as the date from the first dose of study treatment (either VX-984 or PLD, including the Lead-in Period if available), until the minimum (last dose of study treatment + 30 days, date of death).

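### SAP 15.2 replaces the protocol's definition of a treatment-emergent AE (no worsening limb, different end of window) and Section 7 does not declare it

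*SAP*

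**What the plan says.** Protocol 12.3.5.1 states that treatment-emergent AEs (TEAEs) "are defined as AEs that were reported or worsened on or after the start of study drug dosing through the 28-day Safety Follow-up Visit". It sets up two classes: "AEs will be classified as pre-treatment or treatment-emergent". Protocol 8.1.4 and Table 3-3 place the Safety Follow-up Visit at 28 (± 7) days after the last dose.

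SAP 15.2 gives a different rule: "Treatment-emergent adverse events (TEAEs) are defined as those events with onset dates occurring within the on-treatment period as defined in Section 15". Section 15 runs that period from the first dose, Lead-in included, to the earlier of last dose plus 30 days and death. For events before treatment, the SAP keeps the protocol's wording: "Pretreatment AEs are defined as AEs that were reported or worsened after signing the informed consent form up to the start of study treatment".

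SAP Section 7 opens with "The following changes were made in this IAP" and lists five: Part B is not pursued, exploratory endpoints are not analysed, listings use the same population as the tables, PK analysis is reduced to concentration listings, and the Full Analysis Set is redefined. The TEAE definition is not mentioned.

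**The concern.** The protocol defines a TEAE in full. It refers methodological detail to the SAP, but replacing a stated definition is more than adding detail. Section 7 does record other definitional changes, such as the Full Analysis Set, so a reader who finds nothing there about TEAEs could take the tables to follow the protocol. The SAP also treats worsening unevenly: it counts for pretreatment events and, one bullet later and without a reason, not for treatment-emergent ones.

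The tables affected matter. TEAE incidence, with AEs leading to dose modification or discontinuation, heads the list of primary safety endpoints in the Protocol Synopsis. All analyses in SAP 15.2 rest on TEAEs unless stated otherwise, including the grade 3 or higher, serious, related, fatal, interruption, withdrawal and dose-reduction tables. An AE that starts during screening, is held as a single record, and worsens on treatment to the point of withdrawal or dose reduction would be missing from all of them.

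**Working it through.** No sample size or power figure is involved. The check compares the texts and counts days.

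**Worsening**

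1. AEs are collected from signature of consent (Protocol 13.1.1.3), so some can start before the first dose.
2. If such an AE worsens after dosing, it is a TEAE under Protocol 12.3.5.1. Under SAP 15.2 it is one only if the worsening carries its own onset date.
3. Protocol 13.1.1.3 lists, for each AE, the dates of first occurrence and resolution and a toxicity grade. It lists no date of worsening. The CRF completion guidelines are a separate document (Protocol 11.7.1).
4. Two places support a separate record in some cases. The AE definition in Protocol 13.1.1.1 includes worsening of a preexisting condition after consent. Protocol 13.1.1.2 has clinically significant worsening from baseline in laboratory tests, ECGs, physical examinations and vital signs documented as an AE. Neither says how worsening of an AE that is already recorded is entered.
5. The loss therefore ranges from none (each worsening is a new record) to every AE that starts before the first dose and worsens on treatment (one record, original onset).

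**End of window** (days after last dose)

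- Allowed visit days: 28 − 7 = 21 to 28 + 7 = 35, which is 35 − 21 + 1 = 15 days.
- The SAP window ends on Day 30. The cut at death has no effect, because no AE can start after death.
- Difference = 30 − visit day.

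| Visit day | Number of allowed days | SAP window compared with protocol |
|---|---|---|
| 21 to 29 | 29 − 21 + 1 = 9 | longer by 30 − 29 = 1 to 30 − 21 = 9 days |
| 30 | 1 | equal |
| 31 to 35 | 35 − 31 + 1 = 5 | shorter by 31 − 30 = 1 to 35 − 30 = 5 days |

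The counts add up: 9 + 1 + 5 = 15. They are counts of allowed days, not probabilities. At nominal Day 28 the SAP window is 30 − 28 = 2 days longer. With no visit, collection stops at 28 days (Protocol 13.1.1.3), so again nothing is lost.

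Where the SAP window is longer, it gains little: routine collection ends at the visit, and afterwards only SAEs considered related are to be reported (Protocol 13.1.2.2). Where it is shorter, an AE with onset on Days 31 to 35 that was properly collected up to the visit is neither pretreatment nor treatment-emergent under the SAP.

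**The case against.** The strongest reply is that the main harm depends on CRF rules that are not in these documents. If every worsening is entered as a new AE, an onset-date rule captures it and only the wording differs. Protocol 13.1.1.2 makes this more likely for assessment-based findings, because a dose change or discontinuation is itself a criterion of clinical significance. That stands. It leaves mainly symptom-only AEs exposed, and it does not explain why Section 7 is silent.

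Second, much of the information survives elsewhere. The listing of all AEs carries a TEAE flag (SAP 15.2.1). Discontinuations from each drug are tabulated by reason (10.1), deaths have their own table and listing (15.3.1), laboratory shifts use worst on-treatment grade (15.4), and the DLT summary uses the DLT field on the AE page (15.1). None of these depends on the TEAE flag. This also stands, although a listing does not correct an incidence table and these outputs do not tabulate AEs leading to dose reduction.

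Third, the window change is marginal: on 10 of the 15 allowed visit days the SAP window is equal or longer. An AE starting more than 30 days after the last dose could hardly drive dose reduction or withdrawal. Nor is an unclassified late event unique to the SAP, since a related SAE after the visit falls outside both protocol classes. All of this is right and limits the size of the point.

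A reader might also look to the SAP's missing-date rule as a precedent for counting every AE ongoing at first dose as treatment-emergent. It is not one. For a wholly missing onset date, or a partial one that matches the start of drug, "the onset date will be replaced by the minimum of start of study drug and AE resolution date". That handles an unknown onset. It does not reclassify an AE whose onset is known to precede dosing.

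**Conclusion.** The texts conflict, and the change is undeclared; both follow from the wording alone. The consequence is limited: the TEAE tables would omit on-treatment worsening of an AE that began between consent and first dose, if it is kept as one record, and AEs with onset on Days 31 to 35 when the visit falls that late. The number of events cannot be derived and may be small or zero. The analysis is descriptive and covers Part A only.

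A reader might infer that the SAP understates TEAE incidence overall, or that its window is systematically shorter. The documents do not support either: the window difference runs from 9 days longer to 5 days shorter, and the worsening loss rests on an unseen recording rule. Nor are conditions present before consent at issue: their first worsening after consent meets the protocol's AE definition. The DLT and MTD summaries are unaffected. This should be corrected before the tables are run, but it does not undermine the safety analysis.

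**What to change.** In SAP 15.2, restore the protocol's wording so that an AE reported or worsening after the start of dosing counts, and state that an on-treatment worsening of an earlier AE is a TEAE dated by its own AE record. End the TEAE window at the later of the actual Safety Follow-up Visit and last dose plus 30 days, using last dose plus 30 days where there is no visit. Declare the 30-day extension in Section 7. Confine the change to the TEAE definition: altering the on-treatment period in Section 15 itself would also move the maximum QTcF and LVEF-decrease summaries in 15.6.2 and 15.6.3.

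If the CRF holds no dated worsening, keep the onset-based count as the main table. Beside it, as a sensitivity count only, show AEs with onset before the first dose that were still ongoing at the first dose. This needs only the onset and resolution dates already collected. It over-counts AEs that persist unchanged, which is why it should not be the main result.

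The cost is a few lines of SAP text, one Section 7 entry and minor programming with the visit date. TEAE counts may rise slightly.

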15.2.1 All Adverse Events

AEs will be summarized by worst severity (according to National Cancer Institute – Common Terminology Criteria for Adverse Events [NCI-CTCAE] of the latest version) per subject, using the MedDRA preferred term as event category and primary system organ class (SOC) body term as Body System category.

Unless otherwise stated, AEs will be displayed in terms of frequency tables: PT and primary SOC in alphabetical order.

If an AE is reported for a given subject more than once during treatment, the worst severity and the worst relationship to study treatment will be tabulated.

AEs related to study treatment are those events with relationship missing, possibly related or related.

In case a subject had events with missing and non-missing grades, the maximum of the non-missing grades will be displayed.

The following overall frequency tables will be prepared. In addition the tables will be provided by PT and primary SOC in alphabetical order:

- Any TEAE
- Any related TEAEs
 - VX-984 or PLD related TEAEs
 - o VX-984 related TEAEs
 - PLD related TEAEs
- Any serious TEAEs
- Any non-serious TEAEs
- Any related serious TEAEs
 - o VX-984 or PLD related serious TEAEs
 - VX-984 related serious TEAEs
 - PLD related serious TEAEs
- Any TEAE by NCI-CTCAE severity grade ($\geq 3, \geq 4$)
- Any related TEAE by NCI-CTCAE severity grade ($\geq 3, \geq 4$)
 - o VX-984 or PLD related TEAE by NCI-CTCAE severity grade ($\geq 3, \geq 4$)
 - o VX-984 related TEAE by NCI-CTCAE severity grade ($\geq 3, \geq 4$)
 - o PLD related TEAE by NCI-CTCAE severity grade ($\geq 3, \geq 4$)
- TEAEs leading to death (AEs with Grade 5 or outcome "fatal" if Grade 5 not applicable)
- Any related TEAEs leading to death (AEs with Grade 5 or outcome "fatal" if Grade 5 not applicable)
 - o VX-984 or PLD related TEAEs leading to death
 - o VX-984 related TEAEs leading to death
 - o PLD related TEAEs leading to death

The listing for all AEs (whether treatment-emergent or not) will include all the data fields as collected on the "Adverse Events" CRF pages.

- Dose group
- Subject identification number
- First and last dose dates of VX-984
- First and last dose date of PLD
- Reported Term with SOC and PT
- Start and end date with their corresponding treatment day
- Treatment Emergent Adverse Events flag (N/Y)
- Related to VX-984 flag (N/Y)
- Related to PLD flag (N/Y)
- Serious Adverse Events flag (N/Y)
- DTL flag (N/Y)
- CTCAE Grade
- Action taken on VX-984
- Action taken on PLD
- Outcome of AE

Clinical trial.gov and EudraCT requirements

Summary tables for non-serious AEs excluding SAEs applying frequency threshold of 5% will be provided by dose group and overall.

15.2.2 Adverse Events Leading to Treatment Discontinuation

The following overall frequency tables will be prepared for the AE actions. In addition, tables by PT and primary SOC in alphabetical order will also be provided:

TEAEs leading to temporary discontinuation

- TEAEs leading to temporary discontinuation of either study treatment (either VX-984 or PLD)
- TEAEs leading to temporary discontinuation of both study treatments (VX-984 and PLD)
- TEAEs leading to temporary discontinuation of VX-984
- TEAEs leading to temporary discontinuation of PLD

TEAEs leading to permanent discontinuation

• TEAEs leading to permanent discontinuation of either study treatment (either VX-984 or PLD)

- TEAEs leading to permanent discontinuation of both study treatments (VX-984 and PLD)
- TEAEs leading to permanent discontinuation of VX-984
- TEAEs leading to permanent discontinuation of PLD

TEAEs leading to dose reduction

- TEAEs leading to dose reduction of either study treatment (either VX-984 or PLD)
- TEAEs leading to dose reduction of both study treatments (VX-984 and PLD)
- TEAEs leading to dose reduction of VX-984
- TEAEs leading to dose reduction of PLD

15.3 Deaths, Other Serious Adverse Events, and Other Significant Adverse Events

Analysis Set: FAS/SAF

15.3.1 Deaths

All deaths, deaths within 30 days after last dose, and deaths within 60 days after first dose of study treatment, will be tabulated based on information from the "Long-Term Follow-Up" CRF page.

- Number of deaths
- Number of deaths within 30 days after last dose of study treatment (VX-984 or PLD, whatever is later)
- Number of deaths within 60 days after first dose of study treatment (VX-984 or PLD, whatever is earlier)

In addition, date of death will be provided in individual subject data listing together with selected dosing information (date of first/last administration of study treatment).

• Listing of deaths

Will include columns for:

- AEs with fatal outcome (list preferred terms of AEs with outcome = fatal)
- flag for death within 30 days of last dose of study treatment (VX-984 or PLD, whatever is later)
- flag for death within 60 days of first dose of study treatment (VX-984 or PLD, whatever is earlier)

15.3.2 Serious Adverse Events

SAEs will be summarized for each dose group and overall by SOC and PT in alphabetical order (please refer to Section 15.2.1 for items to be listed).

For these AEs, subject listings of SAEs will be provided in addition.

15.3.3 Other Significant Adverse Event

Not applicable.

15.4 Clinical Laboratory Evaluation

Analysis Set: FAS/SAF

Laboratory values (including corresponding normal ranges) from a local lab will be used for in the analyses. A complete list of laboratory tests is presented in the Appendix 18.1.

Laboratory results will be classified according to the latest version of NCI-CTC as provided by the local laboratory. Additional laboratory results that are not part of NCI-CTC will be presented according to the categories: below normal limits, within normal limits and above normal limits (according to the laboratory normal ranges).

The worst on-treatment grade (i.e. on or after first study treatment administration and within 30 days after last study treatment administration) will be summarized considering only subjects with post baseline laboratory samples: Laboratory tests by NCI-CTC grade (0, 1, 2, 3, 4, any).

NCI-CTC gradable and non-grade lab tests are shown in Table 6 and Table 7.

Tables for NCI-CTC gradable parameters:

- Number and percentage of subjects with any, NCI-CTC grade 0, 1, 2, 3, 4, and grade of 3 or 4 laboratory abnormalities under treatment (worst case)
- Shifts in toxicity grading baseline to worst on-treatment

The highest NCI-CTC grade during the on-treatment period is considered as the worst grade for the summary.

Table 4 NCI-CTC gradable parameters

Category	Parameter (LBTEST)	Parameter code (LBTESTCD)	Name in NCI-CTC	Direction of abnormality
	Serum chemistry			
Electrolytes	Calcium	CA	Hypocalcemia/Hypercalcemia	Low/High
Electrolytes	Magnesium	MG	Hypomagnesemia/ Hypermagnesemia	Low/High
Electrolytes	Phosphorus (Phosphate)	PHOS	Hypophosphatemia	Low
Electrolytes	Potassium	K	Hypokalemia/Hyperkalemia	Low/High
Electrolytes	Sodium	SODIUM	Hyponatremia/Hypernatremia	Low/High

Category	Parameter (LBTEST)	Parameter code (LBTESTCD)	Name in NCI-CTC	Direction of abnormality
Enzymes/cardial	Creatinine Phosphokinase	СК	CPK increased	High
Enzymes/liver	Alanine Aminotransferase	ALT	Alanine Aminotransferase increased	High
Enzymes/liver	Alkaline Phosphatase	ALP	Alkaline Phosphatase increased	High
Enzymes/liver	Aspartate Aminotransferase	AST	Aspartate Aminotransferase increased	High
Enzymes/liver	Gamma- glutamyltransferase	GGT	GGT increased	High
Enzymes/liver	Total bilirubin	BILI	Blood bilirubin increased	High
Metabolism	Glucose	GLUC	Hypoglycemia/ Hyperglycemia	Low/High
Metabolism	Uric acid (1)	URATE	Hyperuricemia	High
Plasma proteins	Albumin	ALB	Hypoalbuminemia	Low
Renal/kidney	Creatinine	CREAT	Creatinine increased	High
Renal/kidney	Creatinine Clearance	CREATCLR	part of Chronic kidney disease	Low
	Hematology			
Platelets	Platelets Count	PLAT	Platelet count decreased	Low
Red blood cells	Hemoglobin	HGB	Anemia/Hemoglobin Low/High	
White blood cells/differential	White Blood Cell Count	WBC	White blood cell decreased/Leukocytosis	Low/High
White blood cells/differential	Absolute Lymphocytes Count	LYM	Lymphocyte count decreased/increased Low/High	
White blood cells/differential	Absolute Neutrophils Count	NEUT	Neutrophil count decreased	Low

- (1) According to CTCAE grade, if uric acid value is between ULN and 590 µmol/L it should be graded as follows:
- Grade 1 if there are no physiologic consequences
- Grade 3 if there are physiologic consequences

Tables for non-CTC gradable parameters:

• Number of subjects with shifts from baseline to worst on-treatment post-baseline normal categories.

The normal categories based on the normal range will be produced with the following categories for all hematology and blood chemistry parameters:

- o Baseline: Low/Normal/High/Missing/Overall
- o Worst On-trial: Low/Normal/High/Missing/Overall

^a For a programming perspective, values between ULN and 590 μmol/L will all be graded as Grade 1 (if any physiologic consequences are observed, it should be completed as an adverse event).

^b Final analysis will be based on the actual data received for the trial, discrepancy with the CTC gradable and non-gradable parameters does not constitute a requirement for IAP amendment.

Table 7: NCI-CTC Non-gradable parameters

Category	Parameter (LBTEST)	Parameter code (LBTESTCD)	Direction of abnormality
	Serum chemistry		
Enzymes/cardial	Lactate dehydrogenase	LDH	High
Plasma proteins	Total protein	PROT	Low
Renal/kidney	Blood Urea Nitrogen	BUN	High
	Hematology		
Red blood cells	Hematocrit	HCT	High/Low
Red blood cells	Mean Corpuscular Hemoglobin	MCH	High/Low
Red blood cells	Mean Corpuscular Hemoglobin Concentration	MCHC	High/Low
Red blood cells	Mean Corpuscular Volume	MCV	High/Low
Red blood cells	Red blood cells (Erythrocytes)	RBC	High/Low
Red blood cells	Reticulocytes	RETI	High/Low
White blood cells/differential	Basophils	BASOLE	High
White blood cells/differential	Eosinophils	EOSLE	High
White blood cells/differential	Monocytes	MONOLE	High/Low

Normal category includes low values for high parameters and high values for low parameters.

Subjects without post baseline laboratory samples will be excluded from analyses with respect to values after the baseline.

All CTC gradable and non-CTC gradable parameters will be listed for each measurement. Parameters will be grouped by category.

Listings will include at least the following items:

- Dose group
- Subject identification number
- First/last dosing date of VX-984 and PLD
- Parameters
- Visit
- Date (Treatment day)
- Analysis value
- SI unit
- Change from baseline
- Reference range status (Low, Normal, High)
- CTC grade (with associated CTC name)

Document No. CCl
Object No. CCl

- Baseline flag (Yes/No)
- Worst value on-treatment flag (Yes/No)

In addition, a listing displaying parameters with at least one value with grade ≥ 3 will be provided. For each subject, only parameters where at least one value has grade ≥ 3 will be displayed (all visits for the corresponding parameter will be displayed).

Coagulation parameters

All coagulation parameters will be tested only at Screening, and will be presented in a listing only.

Urinalysis

All urinalysis and microscopic analysis will be presented in listings only.

